## **List of Abbreviations**

CAM – Complementary and Alternative Medicine

ED – Erectile Dysfunction

SD – Sexual Dysfunction

UI – Urinary Incontinence

IIEF - The International Index of Erectile Function Questionnaire.

IPSS - The International Prostate Symptom Score Sheet

BFI - Brief Fatigue Inventory

FACT-G - Functional Assessment of Cancer Therapy-General

### Study Summary

Title	A Feasibility Study Followed by a Randomized Phase 2 Study of Yoga for Radiation Therapy Side Effects in Prostate Cancer
Short Title	Yoga for Prostate Cancer
Protocol Number	UPCC# 05813
Phase	Feasibility study followed by a randomized Phase II study
Methodology	A single arm pilot followed by a 2-arm study
Study Duration	12 months for Feasibility. 36 months for Phase II
Study Center(s)	Perelman Center for Advanced Medicine
Objectives	The purpose of this study is to ascertain the feasibility of yoga interventions as well as the effect of yoga on radiation-related fatigue, sexual dysfunction and urinary incontinence in patients with non-metastatic prostate cancer.
Number of Subjects	63
Diagnosis and Main Inclusion Criteria	Non-metastatic prostate cancer patients undergoing radiation therapy
Study Product, Dose, Route, Regimen	N/A
Duration of administration	Twice weekly yoga sessions for duration of radiation treatment.
Reference therapy	N/A
Statistical Methodology	The primary hypothesis will be tested using a two-group t-test to compare difference scores between Yoga and control groups.

## **1 Introduction**

This document is a protocol for a human research study. This study is to be conducted according to US and international standards of Good Clinical Practice (FDA Title 21 part 312 and International Conference on Harmonization guidelines), applicable government regulations and Institutional research policies and procedures.

### **1.1 Background**

It is estimated that 241,740 men will be diagnosed with prostate cancer in 2012. From 2005-2009 the median age at diagnosis for cancer of the prostate was 67 years of age; approximately 9.5% between the ages of 45 and 54, 31.6% between 55 and 64, and 35.5% between 65 and 74 years old. (1).

For most cancer patients, the most common side effects of cancer as a disease, and cancer treatment are pain, depression and fatigue (2). Cancer –related Fatigue (CRF) is defined as “a common, persistent, and subjective sense of tiredness related to cancer or to treatment of cancer that interferes with usual functioning (3). CRF differs from everyday life fatigue, which is usually temporary and can be relieved by rest or sleep. The impact of CRF on a patient’s ability to function in daily life is considerable and has been found to adversely affect patients’ quality of life even more than pain (4-8). Fatigue is reported in 40 -75% of cancer patients. The prevalence of CRF increased to 60-93% in patients receiving radiotherapy (RT) (4-6), and when Visual Analogue Fatigue Scales were used, the percentage rose up to 99% (9).

However too many cancer patients suffering from fatigue receive inadequate treatment for their symptoms (2). The National Comprehensive Cancer Network guidelines recommend that integrative non-pharmacologic interventions be implemented for managing CRF. Various studies demonstrated positive effect from physical activity interventions during and after cancer treatment. These studies also showed that exercise is safe and well tolerated by patients during various cancer treatments including radiation therapy (10-13).

Specifically, prostate cancer patients report high levels of urinary and sexual adverse effects with more than half of the patients reporting poor sexual drive (14). Erectile

dysfunction (ED) is defined by the National Institute of Health as “the inability to achieve or maintain an erection sufficient for satisfactory sexual performance” (15). ED is reported in 21% to 85% of patients (16-19). The etiology of ED after RT is still debatable, with studies demonstrating occlusive vascular disease and hemodynamics interferences, nerve damage and or damage to the proximal penile structures, such as the penile bulb, the neurovascular bundle, and the local vascular structures (16, 18). Urinary incontinence (UI) is loss of bladder control. There are several forms of UI. The most common type is stress incontinence, which is caused by a loss of outlet resistance at the bladder neck. UI occurs when the bladder detrusor muscle contracts involuntarily during bladder filling, and is a more common side effect of RT. The prevalence of UI after RT is 24% and may take years to develop (14, 16).

The popularity of complementary and alternative medicine (CAM) has been growing rapidly in the general population with up to 69% of Americans now using some modality of CAM (20). Among cancer patients the prevalence of CAM use has increased two to threefold in the last two decades (21-23). Most cancer patients use CAM hoping to boost their immune system, relieve pain and control cancer and cancer treatment’s side effects (24). The National Center for Complementary and Alternative Medicine (NCCAM) defines CAM as “a group of diverse medical and health care systems, practices and products that are not presently considered to be part of conventional medicine” (<http://nccam.nih.gov/health/whatisacam/>). Research on the use of yoga as a modality for alleviating prostate cancer patients’ side effects has been minimal (25).

“The primary aim of yoga is to restore the mind to simplicity and peace, and free it from confusion and distress. This sense of calm comes from the practice of yogic asanas and pranayama.” B.S. K. Iyengar. Yoga rejuvenates the body, restores natural energy, decreases pain, reduces stress, as well as increases muscular strength and flexibility. Nevertheless, most research done in the past using yoga as a treatment modality used women and breast cancer patients as the treatment groups. Participation of men in yoga may be a challenge. The first goal of our study is to evaluate the feasibility of using yoga as a treatment modality in prostate cancer patients. If successful, we will continue seamlessly to a randomized study to determine the effects of yoga on fatigue as measured by the Brief Fatigue Inventory (BFI). We will also ascertain the effects of yoga on overall

QOL as measured by the Functional Assessment of Cancer Therapy-General (FACT-G) instrument, E.D. and U.I by using the IIEF and IPSS questionnaires respectively. The long-term goal of our study is to determine the approximate effect of yoga on fatigue and QOL to inform a subsequent larger randomized study of yoga compared to a control group of patients receiving standard supportive care. QOL instruments will be administered pretreatment, during treatment, and within a week of the last yoga class or by the end of radiation.

## **2 Study Objectives**

1. To determine the feasibility of implementing yoga interventions for men with non-metastatic prostate cancer undergoing radiation therapy.
2. To examine the effect of yoga on cancer and radiation related fatigue, stress levels and patients' quality of life, in addition to standard of care, during active radiation therapy.
3. To examine the effect of yoga intervention on SD, ED and UI during active radiation therapy.
4. To examine the effect of yoga intervention on caregiver quality of life during patient's active radiation therapy as measured by the FACT-G

### **3 Study Design**

#### **3.1 General Design**

1. This study will have 2 phases, and will consist of a preliminary study of feasibility, and a two-arm, phase 2 randomized study of efficacy, with a go/ no-go decision for phase 2 based on feasibility.
2. Those enrolled in the feasibility study will be part of the yoga treatment arm at analysis time.

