#### **7.1.1 Pilot study**

Feasibility (aim 1) will be declared if we successfully accrue 15 evaluable patients of the first 75 approached. Patients participating in the feasibility portion of the study will move seamlessly into the phase II study. The data from these patients will be included in the phase II trial portion of this study. Given the number of prostate cancer patients historically treated in the Radiation Oncology department, we anticipate that this rate of enrollment would allow completion of the phase II trial within <3 years.

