#### **7.1.2 Randomized phase II trial**

##### **7.1.2.1 Sample size determination**

Our goal is to estimate effect sizes for a larger study. We are setting our recruitment aim for phase 2 up to 48 subjects, a 20% increase from our target enrollment in order to account for potential subject drop out and arrive at N = 40. Inclusion of subject data from

the feasibility portion results in  $N = 55$  up to  $N = 63$  should subject attrition levels prove lower than expected. Two groups (35 v 20) give us power to estimate an effect size for yoga participation with a 95% confidence interval that is approximately 1.1 standard-deviations wide (compared to the SD of the raw measure). For the corresponding caregivers, two groups (20 v 20) give power to estimate a CI that is 1.3 SD wide. The effect will be measured as a time x treatment interaction (difference of difference scores). From our own preliminary data, and from Hwang et al. (2008), we know that the within subject correlation for fatigue measures is approximately 0.5, and that the SD for the difference score will be similar to that of the raw measure at individual time points. For the time x treatment interaction, we will be able to detect a standardized effect size of  $d=0.7$  (0.8 for caregivers) at  $\alpha=0.05$  (one-sided) with 80% power.

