#### **7.1.2.2 Statistical Methods**

This randomized study is a two-arm longitudinal controlled trial of yoga as a means of reducing fatigue over the course of radiation therapy for prostate cancer, with measures taken prior to treatment, during treatment, and in follow-up. The analysis will include the initial subjects from the feasibility study as an addition to the treatment arm, and we will control for any differences between the feasibility group and the randomized treatment arm using indicators. The primary measure, and most secondary measures, are Likert-style summary scores on a 0-10 scale and will be treated as Gaussian. The exception is retention, which is a binomial count of those remaining enrolled to the end.

Prior to performing analyses, standard data cleaning procedures will be applied (e.g., checking for outliers and data entry errors, creating summary scores for analysis, and checking that analysis assumptions are met). The assumptions underlying the statistical methods will be examined through the use of standard tests of normality, and graphical displays (27). All analyses will be conducted using Stata software (Stata Corporation, College Station, TX).

We will calculate descriptive statistics for all variables in the study. For outcome variables, we will summarize by treatment group (Yoga versus control) and by time point. We will also estimate correlations within subject for each of the study measures taken at different times.

The primary outcome for the randomized, phase II study will be the difference score of BFI fatigue while undergoing radiation therapy minus BFI fatigue prior to radiation. The primary hypothesis will be tested using a two-group t-test to compare difference scores between Yoga and control groups. This will be a one-sided test with type-1 error at  $\alpha=0.05$ . Similar analysis will be conducted using BFI fatigue at follow-up versus pre-radiation, and for all of the FACT-G fatigue measures. We will test the difference using a one-sided z-test. The FACT-G analysis will be repeated for caregivers (Aim 4).

Effect sizes will be reported for all outcome measures as standardized differences. The effect size will reflect the time x treatment interaction, and the standard deviations will be adjusted for within-subject correlation to aid in designing a larger study.

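### Fifteen non-randomised feasibility patients join the yoga arm, and the plain t-test, the promised indicator and the 35 v 20 power and precision cannot all hold

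*Combined protocol and SAP*

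**What the plan says.** The Study Summary describes the methodology as "A single arm pilot followed by a 2-arm study". The first stage has no control group, and its target is fixed in section 7.1.1: "Feasibility (aim 1) will be declared if we successfully accrue 15 evaluable patients of the first 75 approached". Section 3.1 then says "Those enrolled in the feasibility study will be part of the yoga treatment arm at analysis time", and section 7.1.1 repeats the intention: "The data from these patients will be included in the phase II trial portion of this study".

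Three further statements govern how these patients are used:

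- **Test** (7.1.2.2, repeated in the Study Summary): "The primary hypothesis will be tested using a two-group t-test to compare difference scores between Yoga and control groups". It is one-sided at 0.05.
- **Adjustment** (7.1.2.2): "we will control for any differences between the feasibility group and the randomized treatment arm using indicators".
- **Precision and power** (7.1.2.1): "Two groups (35 v 20) give us power to estimate an effect size", with a 95% CI about 1.1 SD wide and 80% power at d = 0.7. For caregivers, who have no feasibility supplement, "two groups (20 v 20) give power to estimate a CI that is 1.3 SD wide", with a detectable d of 0.8.

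No section says what the indicators are, how one enters a t-test, or what power and precision are once one is fitted. No section specifies a patient analysis restricted to those randomised.

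**The concern.** A two-group t-test has no place for a covariate, so the test as named cannot make the adjustment promised in the same section. The primary analysis can therefore be run in two ways that give different estimates, and the plan does not settle which before the data are seen.

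The choice matters because the trial is meant to supply an effect size for a larger randomised study. Without the indicator, the comparison is part randomised and part not, and any difference between feasibility and randomised yoga patients passes into the estimate. The plan gives reasons not to assume that difference is zero:

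- The feasibility stage comes first (12 months, before a 36-month phase II), so its patients have no concurrent controls.
- Its patients enrol knowing they will receive yoga. The appendix questionnaire (item 7) itself asks whether the prospect of the no-yoga group deters participation.
- The promise of indicators shows that the authors foresaw a difference.

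With the indicator, that bias is removed, but the printed patient power and precision no longer apply.

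**Working it through.** **Inputs.**

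- Feasibility patients: 15 (7.1.1; also 55 - 40 = 15 and 63 - 48 = 15 from 7.1.2.1).
- Yoga 35, control 20 (7.1.2.1), so randomised yoga = 35 - 15 = 20. Section 4.4 does not state the allocation ratio; 1:1 is inferred from these sizes.
- SD of the difference score = 1 raw SD (7.1.2.1 gives a within-subject correlation of about 0.5 and says the two SDs are similar).
- One-sided alpha 0.05, target power 80%.

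**Step 1: reproduce the plan's figures.** SE = √(1/n₁ + 1/n₂). CI width = 2 × quantile × SE. Power is from the noncentral t.

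- 35 v 20: SE = √(1/35 + 1/20) = √0.0786 = 0.280. CI width is 2 × 1.96 × 0.280 = 1.10 (normal) or 1.12 (t). Power at d = 0.7 is 80.3% (normal) or 79.4% (t).
- 20 v 20 (caregivers): SE = √(1/20 + 1/20) = √0.100 = 0.316. CI width is 1.24 (normal) or 1.28 (t). Power at d = 0.8 is 81.2% (normal) or 79.9% (t).

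Both sets match what is printed. The patient figures are therefore those of a pooled comparison with no indicator.

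**Step 2: add the indicator.** Fit difference score = a + b × yoga + c × feasibility to all 55 patients. The term c absorbs the feasibility mean, so b equals the randomised yoga mean minus the control mean exactly; a simulated data set confirmed this. Var(b) = 1/20 + 1/20 = 0.100, against 0.0786 for the pooled test. The 15 feasibility patients add only residual degrees of freedom (52 against 38).

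| | Stated | 35 v 20, no indicator | 55 patients, indicator | 20 v 20 only |
|---|---|---|---|---|
| SE (SD units) | – | 0.280 | 0.316 | 0.316 |
| Power at d = 0.7 | 80% | 79.4% | 70.5% | 70.2% |
| Detectable d, 80% power | 0.7 | 0.71 | 0.80 | 0.80 |
| 95% CI width (SD, t) | 1.1 | 1.12 | 1.27 | 1.28 |

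If all 48 randomised patients are retained (24 v 24), power at d = 0.7 is 77.2%, detectable d is 0.73 and CI width is 1.16 SD.

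**Step 3: leave the indicator out.** Let δ be the difference in mean BFI change between feasibility and randomised yoga patients, in SD units and positive in yoga's favour. The pooled yoga mean shifts by (15/35) × δ = 0.43δ. The documents give no δ, so the values below are assumptions. Type I error is from 400,000 simulated pooled t-tests per value, with no true effect.

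| Assumed δ | Bias in yoga effect (SD) | One-sided type I error |
|---|---|---|
| -0.5 | -0.21 | 0.7% |
| -0.2 | -0.09 | 2.5% |
| 0 | 0 | 5.0% |
| +0.2 | +0.09 | 8.8% |
| +0.5 | +0.21 | 17.8% |

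With the indicator fitted, simulated type I error stays between 4.9% and 5.1% at δ = -0.5, 0 and +0.5.

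**Step 4: could the data decide whether to pool?** For feasibility v randomised yoga, SE = √(1/15 + 1/20) = 0.342, and the 95% CI half-width on 33 df is 0.695 SD. A two-sided 5% test detects δ = 0.5 with 29.5% power and δ = 0.2 with 8.8%. A non-significant result would not show that pooling is safe.

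**The case against.** The strongest reply is that the indicators are undefined, and that the 20 v 20 result follows only if the tested coefficient is randomised yoga minus control. One could fit the feasibility indicator and then contrast the equal average of the two yoga subgroups with control. The variance is then 0.25 × (1/15 + 1/20) + 1/20 = 0.0792, SE 0.281 and CI width about 1.13 SD; weighting by subgroup size returns 35 v 20 exactly. An indicator model and the printed precision can thus coexist. That is correct arithmetic, but such a contrast leaves the feasibility difference in the yoga effect (half of δ, or 15/35 of it), so it does not deliver the control that section 7.1.2.2 promises.

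Other points have partial force:

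- Pooling is openly prespecified, with one site, one eligibility list and one shared yoga procedure. That makes a small δ plausible but does not establish it, and prespecifying pooling does not specify the estimator.
- The error rates of 9% and 18% rest on assumed δ. That is so; they show sensitivity, not an expected bias.
- The declared aim is to estimate effect sizes, which lowers the weight of the power loss. But bias and CI width are properties of the estimate, and the plan also states a one-sided primary test with a power claim.
- Section 7.1.2.3 defines evaluability by yoga attendance, which controls cannot meet in the same way, so restricting to randomised patients does not by itself give a clean comparison. This stands, as a separate matter.

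**Conclusion.** The concern holds. The printed patient figures are arithmetically right, but only for a pooled comparison that makes no adjustment. Under usual indicator coding, the adjustment that the plan promises reduces the estimate to 20 v 20. Power at d = 0.7 is then about 70% and not 80%, detectable d is 0.80 and not 0.7, and the CI is about 1.27 SD wide and not 1.1. Without the adjustment, 43% of any feasibility-versus-randomised difference becomes apparent yoga effect, in a direction that cannot be known beforehand, and the 5% error rate is not guaranteed.

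The power and precision result rests on standard dummy coding, 1:1 allocation and a difference-score SD equal to the raw SD; it needs no assumed δ. The size of the bias does depend on δ, which the documents do not give. Because this affects the primary estimate and the basis for calling it randomised, it should be settled before analysis.

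**What to change.** - **Sections 3.1, 7.1.1, 7.1.2.2 and the Study Summary:** make the primary analysis the comparison of randomised patients only, about 20 v 20. This is what the promised indicator already estimates, and it lets the two-group t-test stand as written.
- **Section 7.1.2.1:** restate the patient figures as detectable d about 0.8 at 80% power (about 70% power at d = 0.7) and 95% CI width about 1.3 SD. These match what the plan prints for its 20 v 20 caregivers.
- **Sensitivity analysis:** report the pooled 35 v 20 comparison without the indicator, labelled as partly non-randomised.
- **Feasibility v randomised yoga:** report the difference with its CI, descriptively. Do not use a significance test of it to decide whether to pool.

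The cost is wording, with no extra patients or visits, and the feasibility data are still reported. The price is less favourable stated precision, at a level the plan already accepts for caregivers. If 80% power at d = 0.7 is to be kept on randomised patients alone, 26 evaluable per arm (52) would be needed instead of 20 per arm (40).

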#### **3.2 Study Measures**

1. Baseline information will be collected prior to start of yoga therapy. (age, race/ethnicity, marital/partner status, educational history, income, residence location, travel time to facility, method of travel, details regarding co-morbidities, disease stage, detail of their current radiotherapy).
2. The Brief Fatigue Inventory (BFI) questionnaire is a 9 –item scale that will be used to rapidly assess fatigue severity. The first three questions rate the severity of the patient’s fatigue at its “worst”, “usual” and “now” levels over the last 24 hours, with 0 meaning “no fatigue” and 10 being “fatigue as bad as you can imagine”. Six questions assess the amount that fatigue has interfered with different aspects of the patient’s life during the past 24 hours. The interference items include general activity, mode, walking ability, normal work (includes both work outside the home and housework), relations with others, and enjoyment of life. The interference questions are measured on a 0 -10 scale, with 0 being “does not interfere” and 10 being “completely interferes”. Scores on this scale range from 0-10, with a mean score of 4.7 and S.D of 2.8. The BFI questionnaire will be completed by patients at the following time points:
  - a. Prior to start of radiotherapy i.e. on the day of consultation or on the day of simulation or setup.
  - b. Bi-weekly while receiving radiotherapy

- SD. Scores range from 0 to 25. Scores (>20) indicate normal degree of erectile function. Scores 10> indicate moderate to severe erectile dysfunction. The IIEF will be completed by patients at the following time points:
- a. Prior to start of radiotherapy i.e. on the day of consultation or on the day of simulation or setup.
  - b. In the 4th week of radiotherapy (when treatment-related symptoms are expected to peak)
    - i. A treatment week is defined as 5 consecutive days of radiotherapy. If a patient misses treatment for any reason his treatment week is shifted back one day.
  - c. Within a week of the last yoga class or by the end of radiation.
5. The International Prostate Symptom Score Sheet (IPSS) will be used to determine the severity of enlarged prostate conditions and measures UI symptoms. Scores on this scale range from 0 to 35, where a score of 8-19 indicate moderately symptomatic, and 20-35 – severely symptomatic. The 8th question on this scale is on QOL and is assigned a score of 1 to 6, where 6 indicates terrible. The IPSS will be completed by patients at the following time points:
- a. Prior to start of radiotherapy i.e. on the day of consultation or on the day of simulation or setup.
  - b. In the 4th week of radiotherapy (when treatment-related symptoms are expected to peak)
    - i. A treatment week is defined as 5 consecutive days of radiotherapy. If a patient misses treatment for any reason his treatment week is shifted back one day.
  - c. Within a week of the last yoga class or by the end of radiation.
6. Yoga interventions will consist of twice-weekly classes, 75 minutes each that will be offered by a yoga instructor. The simplified poses to be used in this study will

include seated (using a chair), standing, and reclining. Yoga poses can and will be modified based on each subjects specific needs and restrictions. Not all yoga poses will be performed each session. Each session will begin with breathing and centering techniques (taking inventory of the levels of energy, posture, stress, emotions, and breath). Yoga poses will consist of the following:

- Sitting on chair: neck and shoulder series (neck and shoulders side, front and back movements, shoulder rolls, and arms movement), table pose with opposite arm and leg movement, side bend (seated Parighasana), simple chair twist (Bharadvajasana).
- Standing poses: mountain pose (Tadasana Samasthithi), warrior II series (Virabhadrasana II), half moon (Ardha Chandrasana) variation at the wall, front warrior series, forward stretch/ bend variation (Uttanasana).
- Recline poses will include: inverted lake pose (Viparita Karani), bridge pose variation (Setubandha Sarvangasana), recline/ sided bound angle pose (Supta Baddhakonasana), camel pose (Ustrasana) at the wall, modified shoulder stand (salamba sarvangasana), reclining big toe posture with a belt (Supta Padangustasana), and corpse pose (Savasana).

